10.2 METHODS AND TIMING FOR ASSESSING, RECORDING, AND ANALYZING SAFETY PARAMETERS

10.2.1 ADVERSE EVENTS

All AEs, including local and systemic reactions not meeting the criteria for “serious adverse events”, will be captured on the appropriate CRF. In addition, the AE Report Form will be completed by the study coordinator (Appendix B). The AE Report Form includes the following:

- What is known about the therapy
- What is known about previous reported side effects
- If the AE occurred in temporal relation to the therapy
- Whether or not the AE improves or disappears when treatment is stopped
- Whether the AE is worsening of baseline symptoms
- Whether the AE is related to concurrent medical condition or medication use

Once complete, this form will be given to the PI and Co-I, who will review, comment, and sign this form. Completed forms will be placed in the participant’s folder.

In addition, the study coordinator will document any AE occurrence on the AE log (*Appendix D*), which includes information such as the date of the AE, severity, relationship to the treatment (assessed by the PI and Co-I*), actions taken, and outcome(s). The log will be reviewed and

initiated by the PI 72 hours after being completed. All AEs occurring during the clinical trial will be documented appropriately regardless of relationship to tACS. All AEs will be followed to adequate resolution and will be graded for severity and relationship to study treatment. Any medical condition noted at the initial session will be considered at baseline and not reported as an AE.

All AEs will be graded for severity using the following guidelines:

- **ASYMPTOMATIC.** The participant is exhibiting no symptoms due to this event; no treatment needed.
- **MILD.** Event results in mild or transient discomfort, not requiring intervention or treatment; does not limit or interfere with daily activities (e.g., insomnia, mild headache)
- **MODERATE.** Event is sufficiently discomforting so as to limit or interfere with daily activities; may require interventional treatment (e.g., fever requiring antipyretic medication). In the case of a moderate AE, the medical advisor may recommend an over the counter medication.
- **SEVERE AND UNDESIRABLE.** Event results in significant symptoms that prevent normal daily activities; may require hospitalization or invasive intervention (e.g., anemia resulting in blood transfusion).

Changes in the severity of an AE will be documented with the Note to File document (Appendix E) and will be filed in the participant's folder.

***Relationship to Study Products:** The PI and Co-I will together determine whether an AE is associated with the study treatment. The event will be labeled associated if the event is temporally related to the administration of a therapy and no other factors can explain the event. The event will be labeled as not associated if the event is temporally independent of the study treatment and can be explained by external factors, such as major life events.

10.2.1 SERIOUS ADVERSE EVENTS

Serious Adverse Event (SAE): An SAE, as defined by the NIH, consists of adverse events that result in death, require either inpatient hospitalization or the prolongation of hospitalization, are life-threatening, result in a persistent or significant disability/incapacity or result in congenital anomaly/birth defect. Other important medical events, based upon appropriate medical judgment, may also be considered Serious Adverse Events if a trial participant's health is at risk and intervention is required to prevent an outcome mentioned.

All SAEs will be recorded on the Serious Adverse Events Form (Appendix B), documented in the UE/SAE log and reported to the IRB. The SAE Form will be completed by the study coordinator, and includes information relating to the onset and nature of the SAE, relationship to the study treatment, seriousness of the SAE, treatment required as a response to the SAE, and outcome. This form will be filed in the participant's folder at the resolution of the event. The study coordinator will complete the UE/SAE log (Appendix D) which includes information such as the date of the event, time at which the study team was informed of the event, details, when the IRB was notified, and the date that the SAE form was completed.

10.2.2 UNANTICIPATED PROBLEMS

Unexpected Events (UE) will be recorded on the UE/SAE log (Appendix D) and will include information such as the date of the event, when the study team was informed of this event, details of the event, when the IRB was notified, and whether the SAE form was completed. The IRB will be notified of each UE that may occur during the study.

The Office for Human Research Protections (OHRP) considers unanticipated problems involving risks to subjects or others to include, in general, any incident, experience, or outcome that meets all of the following criteria:

- unexpected (in terms of nature, severity, or frequency) given (a) the research procedures that are described in the protocol-related documents, such as the IRB-approved research protocol and informed consent document; and (b) the characteristics of the subject population being studied;
- related or possibly related to participation in the research (in the guidance document, possibly related means there is a reasonable possibility that the incident, experience, or outcome may have been caused by the procedures involved in the research); and
- suggests that the research places subjects or others at a greater risk of harm (including physical, psychological, economic, or social harm) than was previously known or recognized.

If an UE occurs the IRB will be notified and the study will be adjusted as needed to protect the health and safety of the participants. Depending on the nature of the UE, the research protocol, inclusion/exclusion criteria, and informed consent will be changed to reflect the possibility of this event reoccurring. During this time, no new participants will be recruited and the research procedures for currently enrolled participants will be stopped. Each UE will be recorded and reported throughout the study.

10.3 REPORTING PROCEDURES

We will be adopting the following table for reporting procedures:

What Event is Reported	When is Event Reported	By Whom the Event is Reported	To Whom the Event is Reported
Fatal or life-threatening unexpected, suspected serious adverse reactions	Within 24 hours of initial receipt of information	Investigator	Local/internal IRBs
Non-fatal, non-life threatening unexpected, suspected serious adverse reactions	Within 48 hours of initial receipt of information	Study Coordinator	Local/internal IRBs/Institutional Officials, DSMB
Unanticipated adverse device effects	Within 10 working days of investigator first learning of effect	Investigator	Local/internal IRBs
Unanticipated problem that is not an SAE	Within 7 days of the investigator becoming aware of the problem	Investigator	Local/internal IRBs/Institutional officials
All Unanticipated	Within 30 days of the	IRB	OHRP

Problems	IRB's receipt of the report of the UP from the investigator	Investigator	External IRBs
----------	---	--------------	---------------

10.3.1 REPORTING OF PREGNANCY

Pregnancy tests will be administered on Day 1 of Stimulation to all women of child-bearing potential. There are no studies that suggest tACS would interfere with pregnancy. However, should a participant become pregnant during the study, their participation will be immediately terminated and will be sent to consult with the Co-I and medical monitor.

10.4 TYPES AND DURATION OF FOLLOW-UP OF PARTICIPANTS AFTER ADVERSE EVENTS

Medical monitors and Co-I will follow up with participants within one week of an AE.

11 STATISTICAL PLAN

11.1 STATISTICAL ANALYSIS STRATEGIES

Our study design is a AB/BA crossover and we will ensure a washout effect by scheduling 1-3 weeks between stimulation sessions. A continuous outcome approach will be used to analyze the crossover trial data where carryover effects will be assumed to be equal.

Primary outcome: Use kubios software to analyze HRV over before and after stimulation. A standard spectral analysis will be applied to the pre and post intervals, including total power, HF, LF, and HP. Specifically looking at the HF component since it reflects the parasympathetic modulation of the heart rate. Use a repeated measure ANOVA with factor session (1 vs 2) and factor treatment (active vs sham) (R software). We hypothesize a treatment main effect and with no session effect and no interaction.

Secondary outcome: A Mann-Whitney-Wilcoxon rank-sum testMann Whitney U test (R software) will be performed on the self-report VAS pain scale (nonparametric scale) (from DVPRS) before and after stimulation as well as between sessions to analyze any differences in self-report perceived pain. Grouped ANOVAs and unpaired t-tests may also be used to analyze correlations within other self-report measures

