6.3.2 EKG PROCEDURES

To obtain a measure of the heart rate during both stimulation conditions, ECG electrodes as part of the EEG acquisition system are placed on the participant's body. Ideally one electrode will be placed below the left collarbone and a second below the right chest. The EKG will be recorded for the full 40 minutes stimulation session during spontaneous breathing and will be divided into 10 minute intervals for analysis. A standard spectral analysis will be applied to a 10-minute interval, including total power, HF, LF, and VLF. The HF component reflects the parasympathetic modulation of the heart rate.

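### The primary HF outcome is defined in two conflicting ways (pre/post intervals versus 10-minute intervals during stimulation), and the primary ANOVA does not say which response it takes or what the pre value is for

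*Combined protocol and SAP*

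**What the plan says.** Section 11.1 states the primary outcome in terms of time around stimulation: "Use kubios software to analyze HRV over before and after stimulation", and then "A standard spectral analysis will be applied to the pre and post intervals, including total power, HF, LF, and HP". The model follows: "Use a repeated measure ANOVA with factor session (1 vs 2) and factor treatment (active vs sham) (R software". No time factor, change score or baseline covariate is named.

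Section 6.3.2, the only EKG procedure in the document, describes a different recording: "The EKG will be recorded for the full 40 minutes stimulation session during spontaneous breathing". It adds that this recording "will be divided into 10 minute intervals for analysis", and then "A standard spectral analysis will be applied to a 10-minute interval, including total power, HF, LF, and VLF". It does not say which of the four intervals is meant, and it describes no EKG before or after stimulation. Section 7.2 likewise has heart rate recorded throughout stimulation, and calls it a covariate.

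Sections 5.2.1 and 5.2.2 schedule 5 minutes of resting EEG before and after stimulation at each visit. Section 6.3.2 says the ECG electrodes belong to the EEG acquisition system, but no section says that HRV is taken from those resting recordings. The primary hypothesis in section 2.4.1 compares active with sham and names no time window.

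**The concern.** The primary endpoint should be one number per participant per session, and the documents do not fix that number. Followed literally, section 11.1 analyses intervals for which no EKG recording is described, while section 6.3.2 records intervals that section 11.1 does not analyse. This is more than a matter of precision: HF during stimulation and HF after stimulation answer different questions.

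If section 11.1 stands, a gap remains. It collects a pre and a post value, but its ANOVA has only session and treatment. Post-stimulation HF and change from pre both fit the wording. They target the same treatment effect but can differ greatly in precision.

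Two things are at stake. Section 11.2 says the results will be used to size later trials, which requires knowing the response behind the estimate and its confidence interval. And an open choice of response allows the primary test to be run in more than one way.

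**Working it through.** **Setting the sections side by side**

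| Item | Section 11.1 | Section 6.3.2 |
|---|---|---|
| When | before and after stimulation | during the 40-minute stimulation |
| Interval length | not stated | 10 minutes (40/10 = 4 intervals) |
| Which interval | pre and post | one of four, not named |
| Role of pre value | none in the ANOVA | no pre recording described |

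Both sections are complete prose, so broken extraction does not explain the difference. Appendix A does not settle it: it has no EKG or EEG row, but its rows are generic and one is an unfilled placeholder.

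**What the choice of response can do**

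There is no power figure in the plan to reproduce; section 11.2 declines to calculate one. From the documents: 20 participants, AB/BA. Assumed: 10 per sequence, two-sided 0.05, an effect of 0.5 SD on the post value only, and unit variance of a single HF value split into participant / session / residual parts (P/S/R).

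For each participant take D = session 1 minus session 2, and regress D on sequence coded +1 (active first) or −1 (sham first). With treatment effect τ and session effect π, the mean of D is π + τ or π − τ. The sequence coefficient is therefore τ and the intercept is π. Its standard error is √(Var(D)/20).

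- Post only: Var(D) = 2(S + R), 18 df.
- Change: Var(D) = 4R, 18 df.
- Post adjusted for pre: Var(D) = 2(S + R)(1 − ρ²), where ρ = S/(S + R) is the correlation of the pre and post session differences, 17 df. The adjusted power below comes from simulation.

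| P/S/R | SE post | SE change | Power post | Power change | Power adjusted |
|---|---|---|---|---|---|
| 0.7/0/0.3 | √(0.6/20) = 0.173 | √(1.2/20) = 0.245 | 78% | 49% | 75% |
| 0.6/0.2/0.2 | √(0.8/20) = 0.200 | √(0.8/20) = 0.200 | 66% | 66% | 75% |
| 0.5/0.4/0.1 | √(1.0/20) = 0.224 | √(0.4/20) = 0.141 | 56% | 92% | 92% |

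Post beats change by 29 points in the first row and loses by about 35 in the last. The adjusted response is near or above the better of the two in each row.

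At ρ = 0 the adjusted 95% CI averaged 0.742 wide against 0.719 for post only: 0.742/0.719 = 1.03, about 3% wider. The covariate starts to narrow the interval relative to post only once ρ exceeds about 0.25.

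**False positives.** With no effect, each test alone rejects about 5% of the time. Reporting whichever of post or change is significant rejects 8–9% of the time (simulation over eight splits with session share 0 to 0.3).

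**Carryover.** Section 11.1 states: "A continuous outcome approach will be used to analyze the crossover trial data where carryover effects will be assumed to be equal". If that fails, the responses fail differently. With 0.6/0.2/0.2, a true effect of 0.50 and an active-treatment carryover of 0.5 SD into both session 2 values, mean estimates were 0.25 (post), 0.37 (adjusted) and 0.50 (change). With carryover into the session 2 pre value only, they were 0.50, 0.62 and 0.75.

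**The case against.** The strongest reply is that the sections can be reconciled. The ECG electrodes are part of the EEG system, and that system records for 5 minutes before and after stimulation. Section 11.1 sets no interval length, so its pre and post HRV could come from those recordings. This is plausible, and a reader should not infer that pre and post EKG is impossible or was never intended. But no section says it, and it would leave the 10-minute intervals of section 6.3.2 without a place in the primary analysis. The contradiction stands.

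A second reply is that the power figures depend on the variance split chosen. That is right. The documents give no variances, so the figures show that the choice can matter in either direction; they do not bound its effect in this trial.

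A third is that a pilot needs less. That covers the missing sample size calculation. It does not cover an undefined primary response when the results are meant to size later trials.

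Two stronger readings are tempting and not supported. One is that pre and post values will both enter the two-factor ANOVA with no time term, which would dilute the effect; the plan nowhere says so. The other is that the plan uses its interaction hypothesis ("We hypothesize a treatment main effect and with no session effect and no interaction") to defend equal carryover. In AB/BA the session-by-treatment term is the between-participant sequence contrast, so it could not serve that purpose. But section 11.1 simply assumes equal carryover and does not claim the interaction supports it. This is a wording note, and it changes no treatment estimate.

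**Conclusion.** The concern holds. Sections 11.1 and 6.3.2 contradict each other on the primary HF outcome, and the ANOVA in 11.1 leaves both the response and the role of the pre value open. That conclusion rests on the text alone.

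The size is illustrative and rests on the assumed 0.5 SD effect, 10 per sequence, two-sided 0.05 and the variance splits shown. Under these, the choice of response can move power by about 30 points or more in either direction, and an after-the-fact choice between post and change raises the false-positive rate from 5% to about 8–9%. It does not follow that the ANOVA is biased as written: with equal carryover, post only, change and adjusted all target the same effect. The plan should be corrected before the data are analysed, and before recording starts if pre and post EKG is to be collected.

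**What to change.** 1. Reconcile sections 5.2.1, 5.2.2, 6.3.2 and 11.1 on when EKG is recorded and how long the analysed interval is.
2. Define one HF response per session. If section 11.1 stands, state that EKG is recorded with the existing 5-minute resting EEG before and after stimulation, and use post-stimulation HF. If section 6.3.2 stands, use the mean HF over the four 10-minute intervals.
3. Make the primary test the sequence coefficient (+1 active first, −1 sham first) from a regression of the session 1 minus session 2 HF difference on sequence. Include the session 1 minus session 2 difference in pre-stimulation HF as covariate if it is recorded; otherwise fit the same model without it. The heart rate that section 7.2 calls a covariate is recorded during stimulation and cannot stand in for the pre value.
4. Report the estimate with its 95% CI.
5. As a minor wording change, label the interaction as the sequence contrast or drop it.

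The cost is some protocol and SAP wording and one regression in R. Since the ECG electrodes are part of the EEG system, recording EKG with the resting EEG should need no new equipment. The covariate costs one degree of freedom and, with 10 per sequence, a CI about 3% wider than post only if the pre and post session differences are uncorrelated. No option is free of the carryover assumption: if carryover is unequal, the covariate can reduce bias or add it.

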2.4.1 SECONDARY OBJECTIVE

NULL HYPOTHESIS. There is no difference in self-reported perceived pain rating between baseline and the active stimulation.

ALTERNATIVE HYPOTHESIS. There is a difference in self-reported perceived pain rating between baseline and active stimulation.

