4 BASIC STUDY DESIGN

This study is a pilot clinical trial with a randomized, double-blind, crossover design. This is a single site study with 2 arms. We estimate six months to complete study enrollment.

Figure 1.

Active sham treatment will include 10 seconds of ramp-in to 1 minute of 10 Hz tACS with a ramp-out of 10 seconds for a total of 80 seconds of stimulation. The choice of an active sham is motivated to enhance success of patient blinding by mimicking skin sensations associated with tACS. 10 Hz tACS will have a 10 second ramp-in and ramp-out with 40 minutes of stimulation for a total of 2420 seconds of stimulation. Stimulation waveform is a sine-wave with peak-to-peak amplitude of 2 mA. In both arms, participants will stay in a relaxed yet controlled state by watching a nature movie (“Reefscape”) during stimulation.

Eligible participants who complete this clinical trial will have a total of 2 visits; 2 days of stimulation (with 1-3 weeks in between). Day one of stimulation will take approximately 2.5 hours as eligibility will be confirmed at the beginning. Day 2 of stimulation will take approximately 2 hours. Two days after each stimulation day, participants will receive via email a follow-up survey to complete that will take approximately 15 minutes. We estimate that total participation will be approximately 6 hours over the course of 6 weeks. All time estimates take into consideration breaks and time variance in administration.

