5.1.2 INITIAL SCREENING SESSION (VISIT 1)

At day 1 of stimulation, participants will be guided through the consent form and the HIPAA authorization form and be given the time to ask any questions about the information discussed. To ensure that all aspects of the research are understood, participants may be asked a series of questions about the research they are about to take part in (*Appendix E*). Once it is clear that the participant understands the consent form and HIPAA authorization, they may sign the forms.

Following the consent process, the participant completes the ODI and DVPRS to measure disability and pain intensity on 0-11 scale. The HAM-D and DASS-21 will assess low suicide risk and depression level. The self-report measures: UCLA Activity Score, PCS, and PSEQ will assess physical activity limitations, pain experience, and confidence in daily activities. Data on demographics, handedness, stai, bis-bas, and opinion pre-treatment will also be collected.

Once eligibility has been confirmed and all relevant data collected, Day 1 of stimulation will begin.

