5.3 FOLLOW-UP

5.3.1 FOLLOW-UP EMAIL

Two days after both sessions of stimulation, participants will receive an email with a follow up survey to assess any change in pain perception. The ODI and DVPRS will take approximately 15 minutes to complete.

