6.3 SPECIAL ASSAYS OR PROCEDURES

6.3.1 SPECIAL PROCEDURES

Each participant will attend two days of stimulation for this study. Each participant will be randomly assigned to one of two treatment arms (sham or 10 Hz tACS) then the opposite on the second visit. For more information on the stimulation procedures, see section 7.2 *Preparation and Administration of Study Investigational Product*.

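### Section 11.1 gives the before-versus-after pain comparison an independent-samples rank-sum test, although it compares the same participants with themselves

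*Combined protocol and SAP*

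**What the plan says.** Section 11.1 sets the test for the secondary outcome: "A Mann-Whitney-Wilcoxon rank-sum testMann Whitney U test (R software) will be performed on the self-report VAS pain scale". The scores come from the DVPRS, and the comparisons are "before and after stimulation as well as between sessions to analyze any differences in self-report perceived pain". The same section opens with a general statement on the crossover data: "A continuous outcome approach will be used to analyze the crossover trial data where carryover effects will be assumed to be equal". It gives the primary HRV outcome a repeated-measures ANOVA, and it allows grouped ANOVAs and unpaired t-tests for other self-report measures.

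The secondary null hypothesis (section 2.4.1) is: "There is no difference in self-reported perceived pain rating between baseline and the active stimulation". Section 6.3.1 confirms that everyone receives both conditions: "Each participant will be randomly assigned to one of two treatment arms (sham or 10 Hz tACS) then the opposite on the second visit".

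The DVPRS is given before stimulation at both visits (sections 5.1.2 and 5.2.2). Neither stimulation-day section lists it after stimulation. The only later DVPRS is in the e-mail survey two days after each session (section 5.3.1): "The ODI and DVPRS will take approximately 15 minutes to complete". Section 3.1 requires a VAS pain score above 4 at entry, and section 6.1 gives the DVPRS an MCID of 2 points.

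**The concern.** The rank-sum and Mann-Whitney U tests are two names for one test, which treats its two sets of scores as coming from different people. Before versus after stimulation compares two scores from the same people. If those scores are positively correlated, the standard error built into the test is too large for the difference being tested, so p-values are too large and a real change in pain is easier to miss. Only 20 participants are planned, so the precision that the pairing offers matters. The wording does not look like a slip for the paired test: both names given are those of the unpaired one, and the next sentence also speaks of unpaired t-tests.

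The sentence also leaves open which score is the one after stimulation, so the test cannot be run as written without a further choice.

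**Working it through.** **No figure to reproduce.** Section 11.2 declines a sample size calculation, and the plan states no alpha, SD, correlation or power.

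**Inputs from the documents.** 20 participants (section 3), hence 20 pairs if all complete; a two-sided hypothesis (section 2.4.1); MCID 2 points (section 6.1); entry score above 4 (section 3.1).

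**Assumptions.** Alpha 5%; mean pain 6; SD 2 or 2.5; one common within-person correlation ρ of 0.3, 0.5 or 0.7; scores rounded to a 0-10 scale.

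**Step 1: direction, by normal approximation.** An unpaired test uses a standard error of σ√(2/n). The true one is σ√(2(1−ρ)/n), smaller by the factor √(1−ρ). The actual type I error is therefore about 2Φ(−1.96/√(1−ρ)):
- ρ = 0.3: 2Φ(−1.96/0.837) = 1.9%
- ρ = 0.5: 2Φ(−1.96/0.707) = 0.6%
- ρ = 0.7: 2Φ(−1.96/0.548) = 0.03%

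Unpaired power is about Φ((δ/(σ√(2/n)) − 1.96)/√(1−ρ)). For δ = 1 and σ = 2, δ/(σ√(2/20)) = 1.581, which is below 1.96. A higher ρ then lowers power: 32.5, 29.6 and 24.5%. The paired formula, Φ(δ/(σ√(2(1−ρ)/n)) − 1.96), gives 47.2, 60.9 and 82.3%. The approximation is optimistic for rank tests on rounded scores, so the sizes below come from simulation.

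**Step 2: simulation, no selection on baseline.** 4,000 trials per cell (20,000 for the no-effect row). Entries are rank-sum / signed-rank rejection rates in %.

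| Case | ρ 0.3 | ρ 0.5 | ρ 0.7 |
|---|---|---|---|
| No effect, SD 2 | 1.9 / 4.5 | 0.7 / 4.1 | 0.1 / 4.6 |
| 1 point, SD 2 | 28.4 / 40.0 | 27.0 / 51.6 | 23.5 / 73.5 |
| 2 points, SD 2 | 87.0 / 92.4 | 91.2 / 97.9 | 95.5 / 100 |
| 2 points, SD 2.5 | 67.6 / 78.0 | 70.3 / 89.7 | 77.3 / 98.8 |

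The loss at the MCID is 92.4 − 87.0 = 5.4, 6.7 and 4.5 points at SD 2, and 10.4, 19.4 and 21.5 at SD 2.5. At 1 point and SD 2 it is 11.6, 24.6 and 50.0. A repeat with 8,000 trials per cell agrees. At SD 2.5 and 1 point it gives 18.2 / 26.5, 14.8 / 36.0 and 11.0 / 52.5, a loss of 8 to 42 points.

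Section 5.1.2 describes the scale this way: "the participant completes the ODI and DVPRS to measure disability and pain intensity on 0-11 scale". A run on 0-11 at SD 2 gives the same picture: loss 5 to 8 points at the MCID and 12 to 50 at 1 point.

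**Step 3: the visit-1 DVPRS is also the entry score above 4.** 10 participants per sequence, active condition, before versus after.

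| Case | ρ 0.3 | ρ 0.5 | ρ 0.7 |
|---|---|---|---|
| No effect, SD 2 | 4.0 / 7.2 | 1.9 / 6.4 | 0.5 / 5.2 |
| 1 point, SD 2 | 54.1 / 62.4 | 50.4 / 70.5 | 50.7 / 84.1 |
| 2 points, SD 2 | 97.3 / 98.4 | 98.5 / 99.7 | 99.5 / 100 |
| 2 points, SD 2.5 | 90.3 / 92.9 | 92.8 / 97.4 | 94.9 / 99.6 |

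The MCID loss shrinks to about 1 point (SD 2) or 3 to 5 points (SD 2.5). With no effect, mean pain still falls by 0.28, 0.20 and 0.12 points through selection alone. That is why the signed-rank test exceeds 5%, and part of the 8 to 33 point gap at 1 point reflects this drift.

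**Step 4: other correlations.** At ρ = 0 nothing is lost (5.3 / 5.1% with no effect, SD 2). At ρ = −0.3, unlikely for repeated pain scores, the rank-sum test rejects too often (7.6%).

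**The case against.** **The general crossover sentence may cover pain.** A rank-sum test is valid in an AB/BA design when it compares participants' period differences between the two sequences. But the pain sentence mentions neither period differences nor sequences; it applies the test to the scale itself. Nor would that reading supply a paired test for before versus after, which is the stated hypothesis.

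**The between-sessions comparison.** A reader might infer that it is active versus sham and equally at fault. The documents do not settle this. Section 11.1 separates session (1 vs 2) from treatment (active vs sham), so it may mean visit 1 versus visit 2, or a comparison of before-after changes. On pooled post-stimulation scores, with the entry rule and SD 2, the rank-sum test would lose power for active versus sham at 1 point (30.0, 30.0 and 35.1%, against 38.5, 51.0 and 72.4% for period differences between sequences). On pooled change scores it loses nothing under the common-correlation model (25.2, 31.4 and 48.0%, against 23.4, 29.0 and 44.2%). This objection stands: only the before-versus-after fault is established.

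**Selection at entry.** Section 4 places the eligibility check at the start of day one: "Day one of stimulation will take approximately 2.5 hours as eligibility will be confirmed at the beginning". The visit-1 DVPRS could therefore be the entry score, in which case the MCID loss is slight. This also stands, though the documents do not say that the two scores are the same.

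**Low stakes.** This is a secondary outcome in a pilot with no power claim and no decision rule tied to the pain p-value. Under positive correlation the test errs towards caution. That limits the weight of the point but does not make the test right.

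**Conclusion.** The point holds for before versus after stimulation: the plan names an unpaired test for a paired comparison. Under positive within-person correlation the cost is a type I error of about 0.1 to 2% in place of 5%. The power loss at the MCID runs from about 1 point (SD 2, baseline selected) to about 22 points (SD 2.5, ρ = 0.7, no selection). For a 1-point effect at SD 2 it is 8 to 33 points with selection and 12 to 50 without. All sizes depend on assumed SDs and correlations. The 1-point effect is illustrative; the plan's only anchor is 2 points.

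A reader might go further and infer that the plan invites false positive pain findings, or spoils the pilot's input to a later sample size. Neither follows. Under positive correlation the test is conservative, and the choice of test changes neither the observed pain change nor the SD of within-person differences. It should be fixed because the remedy is cheap, but it is a modest fault in a secondary analysis, and the primary HRV analysis is untouched.

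**What to change.** In section 11.1:

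- For before versus after within a condition, replace the rank-sum test with a Wilcoxon signed-rank test or a paired t-test.
- State which DVPRS is the after-stimulation score. The only one now scheduled is the two-day e-mail survey.
- Note that this uncontrolled change includes regression to the mean from the entry rule, so it is not by itself evidence of a treatment effect.
- State what the between-sessions comparison is. If it is active versus sham, use a crossover analysis that allows for period: a rank-sum test of period differences between the AB and BA sequences, or a mixed model with participant, period and treatment.
- Choose post-stimulation or change scores in advance, without claiming that either has more power. Post scores do better under a common correlation. Change scores do better when correlation within a visit is clearly higher than between visits (1-point effect, SD 2: 59% against 48% at 0.8 within and 0.4 between; 83% against 60% at 0.9 and 0.6).
- Use paired or mixed-model methods for other self-report scales repeated within participant, such as the ODI. Unpaired tests may stay for between-participant groupings such as BDNF status.

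The cost is wording only, with the same data and software, provided the two-day score is the one meant. If a same-day rating was intended, an assessment would have to be added.
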